3.7 Informed Consent

Institutional Review Board (IRB) approved informed consent forms will be presented to the patient, and informed consent must be obtained prior to enrolling the patient in this randomized controlled trial. The full list of potential risks to the patient and her neonate will be listed in the informed consent. The nature and purpose of the study will also be detailed in the informed consent. The patient will be provided a copy of the signed informed consent. The informed consent will only be in English, and thus, only English-speaking individuals may participate in the study.

4. Study Procedures

4.1 Screening for Eligibility and Consent

All patients will be identified utilizing the IRB-approved UAB Obstetric Automated Recording (OBAR) system (IRB X030604010). This system will be used to identify patients entering the 37th-42nd week of pregnancy. Those initially meeting eligibility criteria by chart review will be called via the “phone script” (see phone script attached). If the patient continues to meet eligibility criteria after completing the “phone script,” she will be scheduled in the UAB Obstetrics Complications Clinic (OBCC) for her next appointment (between 37th-42nd weeks of gestation) where a co-investigator will present the study which will include the risks, benefits, procedures, and alternatives. The informed consent will be signed after all questions have been answered. The induction of labor will not be conducted prior to 39+0 weeks’ gestation.

4.2 Randomization

Randomization will occur after eligibility/exclusion criteria are confirmed and informed consent is obtained. Randomization will occur by a predetermined computer-generated block randomization scheme prepared by a study statistician. A variable block design will be utilized.

Women randomized to the standard inpatient (control) group will be scheduled for cervical ripening in the UAB Women and Infants Center. The patients randomized to the outpatient (intervention) group will undergo placement of the transcervical Foley catheter per the protocol, and a scheduled time to report to the UAB Women and Infants Center the following morning for their induction of labor will be given to the patient.

4.3 Management of patients in whom the transcervical Foley catheter cannot be placed

A patient who has a cervix completely closed where a transcervical Foley catheter cannot be traversed is at a high likelihood of having a failed induction of labor. Thus, if the transcervical Foley catheter is unable to be placed, regardless of the assigned group, the patient will be scheduled to return in 24-72 hours for another attempt. This will allow additional time for the cervix to ripen naturally and therefore increase the patient’s likelihood of having a successful induction of labor.

4.4 Management of patients who cannot tolerate placement of the transcervical Foley catheter

Some patients may not tolerate placement of the transcervical Foley catheter. If patients are between 39-40^{6/7} weeks, they will be offered the option of withdrawing from the study and returning in spontaneous labor as long as fetal heart rate tracing is Category I. We will request permission from patients withdrawing from the study to assess labor and delivery outcomes. If patients are inpatient, they will be offered epidural placement or intravenous pain medications

If the patient cannot tolerate the placement of the transcervical Foley catheter, she will be induced by another method. Since the analysis is intent to treat, the patient will remain in the assigned group.

4.5 Adherence

Patients in either group may request to have the transcervical Foley catheter removed at any time secondary to discomfort if conservative measures, such as acetaminophen, do not relieve the discomfort. If a patient in the outpatient (intervention) group presents to the MEU with complaints of pain, she will be admitted and cervical ripening/induction of labor will continue. If the transcervical Foley catheter extrudes from the vagina while the patient is at home, she will be instructed to place it in a provided bag and write down the time it extruded from her vagina.

4.6 Participant follow-up

Patients will be followed-up once during their postpartum inpatient hospitalization. This follow-up will be done post-delivery and before their discharge and will include a short series of surveys evaluating patient satisfaction regarding inpatient and outpatient cervical ripening. Investigators and principal investigators experienced in abstracting obstetrical and perinatal outcomes will review the patients' and neonates' charts after delivery to abstract the necessary variables to satisfy the primary and secondary outcomes. No further patient follow-up will occur after discharge from the UAB Women and Infants Center.

4.7 Adverse Event Reporting

A Data Safety Monitoring Board (DSMB) will be formed and consist of three individuals within the Division of Maternal-Fetal Medicine and Department of Pediatrics who have no ties to the study design, evaluation of results or potential authorship of the manuscript. The primary purpose of the DSMB will be to monitor patient safety. The members of this board are Drs. [name] (obstetrician), [name] (epidemiologist), and [name] (pediatrician).

The purpose of the study is to determine whether outpatient cervical ripening shortens the admission to delivery timing compared to the standard inpatient method. The safety of a transcervical Foley catheter has already been established, and it does not increase the risk of adverse events such as chorioamnionitis, placental abruption, non-reassuring fetal heart rate tracings, cesarean section, or stillbirth.

We define an adverse event as an undesirable experience or outcome occurring in a research participant, regardless of whether participation in the research study caused the event to occur. For example, placental abruption and/or stillbirth are known risks of pregnancy, and while not known to be related to transcervical Foley catheter usage, would be considered an adverse event if it occurred during the study. All serious adverse events will be reported to the DSMB and IRB. A serious adverse event will include the following events.

- a. Death
 - a. Maternal
 - b. Fetal (stillbirth)

- b. Life-threatening
- c. Prolonged hospitalization
- d. Disability or permanent damage
- e. Intervention required in an attempt to prevent permanent impairment or damage (i.e. non-reassuring fetal heart rate tracing while the transcervical Foley catheter is in place necessitating an emergent delivery.
- f. Other serious or important medical events:
 - a. Placental abruption
 - b. Chorioamnionitis diagnosed while the transcervical Foley catheter remains in place
 - c. Any other serious event necessitating a higher level of care, such as a transfer to an intensive-care unit.
- g. Any other event not listed that the investigators believe may have been caused by the intervention.

4.8 Study Outcome Measurements and Ascertainment

4.8.1. Primary outcome

The primary outcome is the time from admission to delivery.

4.8.2. Secondary outcomes

- a. Patient satisfaction
- b. Placental abruption
- c. Early admission for intractable pain (outpatient group)
- d. Intractable pain requiring epidural anesthesia while the transcervical catheter remains in situ
- e. Non-reassuring fetal heart rate tracing upon admission in the outpatient group
- f. Non-reassuring fetal heart rate tracing while the transcervical catheter remains in place requiring immediate delivery
- g. MEU visits prior to scheduled admission time (outpatient group)
- h. SROM occurring in the outpatient group prior to scheduled admission time
- i. Chorioamnionitis or endometritis
- j. Total time of epidural use
- k. Mode of delivery
- l. Total time of oxytocin infusion
- m. Total cumulative dose of oxytocin infused
- n. Maximum rate (milliunits/min) of oxytocin infused
- o. Labor and delivery charges
- p. Composite neonatal outcomes
 - a. Apgar score < 7 at 5 minutes
 - b. Arterial cord blood gas pH < 7.1
 - c. Arterial cord blood gas base deficit > 12

- d. Admission to the neonatal intensive care unit.

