5.5. Interim Monitoring

We propose an interim analysis when 32 patients in each group have completed the study (50% completion) to determine whether continuation of the study is necessary. We do not propose a formal stopping rule for safety, but the DSMB will continually monitor the study for safety.

6. Future studies

If our results show outpatient transcervical Foley catheter placement is safe, well-tolerated, and reduces hospital admission time to delivery, we will submit a Patient Centered Outcomes Research Institute (PCORI) grant to conduct a multi-center trial in an attempt to alter current induction methods and ultimately improve patient satisfaction and outcomes.

7. References

- 1) World Health Organization: WHO recommendations for induction of labour, Department of reproductive health and research. Geneva, Switzerland: World Health Organization; 2011:32.
- 3) Wing DA. Labor induction with misoprostol. *Am J Obstet Gynecol* 1999 Aug;181(2):339-45.

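### Epidural with the catheter in place (item d) is the only explicit pain outcome comparable between arms, but outpatients can meet it only after admission, so it measures access to epidural as well as pain

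*Combined protocol and SAP*

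**What the plan says.** All references are to the combined protocol and SAP.

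- **Pain outcomes (4.8.2).** Item c, early admission for intractable pain, is limited to the outpatient group. Item d is "Intractable pain requiring epidural anesthesia while the transcervical catheter remains in situ", with no arm restriction. Two other outcomes cover both arms and might reflect pain. One is item j, "Total time of epidural use", which is not tied to the catheter. The other is satisfaction (item a), which 4.6 describes as a "short series of surveys evaluating patient satisfaction regarding inpatient and outpatient cervical ripening"; the survey items are not given.
- **Where catheter time is spent (3.3, 3.6).** Controls have the catheter placed after admission to labor and delivery. Outpatients have it placed at a study visit, are monitored for 30 more minutes and go home until the next morning. A catheter still in place at admission may stay until 24 hours after placement, and management is then the same as for controls.
- **What happens with pain (4.5).** "If a patient in the outpatient (intervention) group presents to the MEU with complaints of pain, she will be admitted", and ripening continues. Also, "Patients in either group may request to have the transcervical Foley catheter removed at any time secondary to discomfort". Removal for discomfort is not a listed outcome.
- **Use of the results.** Section 3.2 b lists epidural with the catheter in place among adverse outcomes to be assessed in both groups. Section 1.2 b hypothesizes that outpatient ripening will not increase adverse outcomes. Section 5.4 gives event comparisons a chi-square p-value, relative risk and confidence interval. Section 6 sets the conditions for a multicenter application: "If our results show outpatient transcervical Foley catheter placement is safe, well-tolerated, and reduces hospital admission time to delivery".

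**The concern.** The same pain can score differently by arm. A control with intractable pain can be given an epidural and scores one on item d. An outpatient with the same pain at home scores on item d only if she is admitted and then has an epidural while the catheter is still in place. If the catheter is removed at her request, or comes out before she arrives, she scores zero. Her early admission counts under item c, which has no control counterpart, and a removal counts nowhere.

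At stake is how the trial's tolerability result is read. The hypothesis is one of no increase, so a relative risk near or below 1 on item d would be taken as support. The distortion runs in that direction. It does not have to reach significance to mislead, because it can also hide a real excess of pain at home.

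**Working it through.** **1. The plan's own figure.** The only sample size is for the primary outcome (5.1): alpha 0.05, power 80%, SD 24 h, difference 12 h. With a two-sided test, 2 × (1.960 + 0.842)² × (24/12)² = 62.8, so 63 per group. The t-test version gives 63.8, so 64, with power 0.801. The stated 64 reproduces. No figure is given for item d; section 5.2 says power for secondary outcomes is limited, except for satisfaction.

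**2. What item d estimates.** Let p_c and p_o be the true risks of intractable pain with the catheter in place (control, outpatient). Let s_c and s_o be the shares of those cases that become an epidural with the catheter still in place. Then

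observed RR = (p_o × s_o) / (p_c × s_c) = true RR × (s_o / s_c).

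Item d is biased toward fewer outpatient events whenever s_o is below s_c. Taking s_c = 1 (assumption: every control case gets an epidural) and writing s for s_o gives observed RR = true RR × s. If some controls take intravenous medication or have the catheter removed instead, s_c is below 1 and the bias is smaller.

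**3. What determines s.** Let h be the share of outpatient pain cases that arise at home, and c the share of those that become an in-situ epidural after admission. Assume that cases arising after admission all convert. Then s = (1 − h) + h × c. The documents give neither h nor c, so the values below are assumptions.

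| h | c = 0 | c = 0.5 | c = 1 |
|---|---|---|---|
| 2/3 | 0.33 | 0.67 | 1.00 |
| 1 | 0 | 0.50 | 1.00 |

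With an assumed true risk of 15% in both arms and h = 2/3, item d would show 15% in controls against 5%, 10% or 15% in outpatients.

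**4. Chance that the artefact alone gives two-sided p < 0.05.** This takes 64 per arm, the same true risk p in both arms and s_c = 1, by normal approximation. The approximation is rough where events are few: p = 5% means 64 × 0.05 = 3.2 expected control events.

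| p (assumed) | s = 0 | s = 0.25 | s = 0.5 |
|---|---|---|---|
| 5% | 0.44 | 0.23 | 0.11 |
| 10% | 0.74 | 0.42 | 0.19 |
| 20% | 0.97 | 0.73 | 0.35 |
| 30% | >0.99 | 0.91 | 0.53 |

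At s = 1 there is no artefact.

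**5. Masking.** If pain were truly twice as common in outpatients and s = 0.5, item d would show 2 × 0.5 = 1.0.

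**The case against.** A reader might infer that the trial is bound to show better tolerability outside hospital, with a relative risk between 0 and about one third. The documents do not support this. That range is the c = 0 column in step 3: it assumes no woman with pain at home ever goes on to an epidural with the catheter in place. Section 4.5 admits outpatients who present with pain and continues ripening. Section 3.6 lets others arrive with the catheter still in place, and sends some straight to the labor room after placement if the tracing is not Category I, or if significant bleeding or membrane rupture occurs. All of these women can meet item d. This objection stands, so the size of the bias is unknown.

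Four further points count against a strong claim.

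- Section 1.2 states no between-arm direction for item d and expects a small number of events. Section 5.4 does not name item d, so a test on it is a reasonable reading and not an explicit statement. However, 3.2 b places it among adverse outcomes assessed in both groups, under a hypothesis of no increase. The comparison is therefore within the plan.
- Whether outpatient placement is well tolerated is largely a question about the outpatient arm, which items c and g (MEU visits) address. This stands: tolerability is not beyond judgment. But these items have no comparator, and the pain content of the satisfaction survey cannot be seen.
- No section says an epidural is unavailable at home; that is inferred from the setting. The sentence "If patients are inpatient, they will be offered epidural placement or intravenous pain medications" concerns women who cannot tolerate placement, not pain during ripening, and is only indirect support.
- A composite that adds unscheduled admission for pain would not be symmetric, because controls cannot have that event. Since a complaint of pain alone leads to admission under 4.5, it could turn the bias the other way.

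**Conclusion.** The point holds in a limited form. Item d gives the two arms unequal opportunity to have the event. The comparison leans toward outpatient care whenever outpatient pain cases become in-situ epidurals less often than control cases do. That rests on one inference (no epidural at home) and on the text of 3.6, 4.5 and 4.8.2.

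The size cannot be fixed from the documents: at equal true risk, the observed relative risk runs from 1 (all convert) toward 0 (few convert). A significant false difference is likely only if the event is fairly common and few cases convert (0.73 at 20% risk and s = 0.25). It is unlikely if the event is rare and half convert (0.11 at 5% and s = 0.5). Low power does not remove the problem, because a null or favorable result would be read as agreeing with the hypothesis. Item d cannot by itself support either the no-increase hypothesis or the tolerability condition in section 6. The primary analysis and sample size are unaffected.

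**What to change.** In 4.8.2 and 5.4:

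1. Report items c and d descriptively by arm. Put no between-arm test or relative risk on item d as a measure of pain or tolerability.
2. Add catheter removal at the woman's request for discomfort, counted from placement to expulsion or removal, as the between-arm tolerability outcome. Section 4.5 already allows it in both arms. Record the reason for removal, so that removal at the 24-hour limit or for other reasons is not counted.
3. If a composite is also wanted (removal for discomfort, epidural or intravenous medication for pain with the catheter in place, early admission for pain), show each component separately. State that early admission can occur only in outpatients, so the composite is not symmetric.

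The cost is one or two more fields in the chart abstraction that 4.6 already plans. Treatment, sample size and primary analysis do not change. The downsides are few expected events and limited precision. Removal is also not wholly free of setting, since a control may take an epidural and keep the catheter, so it should be read beside items c and d.

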3.6 Study groups

There will be two intervention groups:

a. All patients:

- a. Patients will present to the 2nd floor of the CRWH for a scheduled OFFSITE study visit. This will occur every weekday except Friday.
- b. The order of events in the CRWH for all patients will be as follows:
 - i. Blood pressure evaluation
 - ii. Transabdominal ultrasound
 - iii. Vaginal examination
 - iv. Continuous fetal heart rate and tocometry monitoring for 20 minutes.
- c. If the patient's blood pressure is normal (<140 mmHg systolic and < 90 mmHg diastolic), ultrasound identifies a vertex fetus with normal amniotic fluid, cervix meets inclusion criteria (< 3 cm. If between 2-3 cm, then < 80% effaced), and the fetal heart rate tracing is category 1* without evidence of three contractions in a ten minute period, then the patient will be consented and randomized to either group 1 (standard treatment) or group 2 (intervention) and management will follow as detailed below.
 - i. Patients who do not meet cervical dilation criteria because of not needing cervical ripening (cervix >3 cm, or if 2-3 cm dilated and > 80%) will have their induction of labor canceled unless they are patients of the PrimeCare division.

b. Group 1 (Standard treatment)

- a. The patient will return the next day for her scheduled induction of labor at a pre-assigned time.
- b. Patient will be admitted to the labor and delivery floor and will be registered in the standard fashion by the nurse. The physician will be notified when the patient has had a reassuring fetal heart rate tracing and is ready for placement of the Foley catheter.
- c. The physician will perform an ultrasound to confirm vertex position and check the cervix. The patient will remain in the study even if she no longer meets cervical exam requirements (≤ 3 cm, if 2 cm, < 80% effaced) since the study design is intent to treat.

- d. Using the standard technique (dorsal lithotomy, betadine prep, sterile ring forceps, balloon inflated to 30 ml sterile saline), the transcervical Foley catheter will be placed transcervically. It is at the provider's discretion to tape this to the inner thigh or to leave it un-taped.
 - i. If the transcervical catheter is unable to be placed with a speculum and ring forceps, the provider may place with digital guidance.

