5.3. Analysis Plan

Standard baseline characteristics between the two groups will be collected at baseline. It is assumed that randomization will evenly distribute baseline characteristic differences between the two groups, and thus, we do not anticipate adjusting for these in the primary analysis. Secondary analyses will, though, be analyzed using regression adjustments to account for any possible confounding covariates between the two groups. The primary analysis will be done in an intent-to-treat basis.

The primary analysis will compare the total admission to delivery time in minutes between the two groups. This will be analyzed using a two-sided student's t-test.

5.4. Secondary Aims:

The secondary analyses will be to compare the incidence of certain events between the two groups. A Chi-square p-value, relative risk, and 95% confidence interval will be calculated.

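### Abnormal tracing on admission, MEU visits and membrane rupture before scheduled admission are counted only in outpatients, although controls are also at home then and could give a randomized comparison

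*Combined protocol and SAP*

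**What the plan says.** Section 4.8.2 names the outpatient arm in four secondary outcomes:

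- item c: early admission for intractable pain;
- item e: "Non-reassuring fetal heart rate tracing upon admission in the outpatient group";
- item g: MEU visits before the scheduled admission time;
- item h: "SROM occurring in the outpatient group prior to scheduled admission time".

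Sections 3.2.b and 3.2.c carry the same restrictions.

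Section 3.6 gives all women the same entry checks at one visit and randomizes them there. A woman in the outpatient arm has the catheter placed, is monitored for 30 more minutes and goes home until the next morning. For a control, "The patient will return the next day for her scheduled induction of labor at a pre-assigned time". Once the control is admitted, "The physician will be notified when the patient has had a reassuring fetal heart rate tracing and is ready for placement of the Foley catheter".

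On the analysis, section 5.4 states: "The secondary analyses will be to compare the incidence of certain events between the two groups". The statistics named are a chi-square p-value, a relative risk and a 95% confidence interval.

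**The concern.** Both arms are out of hospital between randomization and scheduled admission, one with a catheter and one without. Women at 39 to 42 weeks may come to triage, rupture membranes or arrive with an abnormal tracing without any catheter. If such events are counted only in the outpatient arm, the reader cannot tell how many would have happened anyway. Background events could make outpatient ripening look worse than it is, or a real excess could pass as background.

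The at-home period is what distinguishes the intervention, and section 6 makes a multicenter proposal depend on showing that the approach is safe and well tolerated. The randomized reference group exists, but the outcome definitions do not use it.

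**Working it through.** **1. The plan's own figure.** Section 5.1 gives alpha 0.05, power 80%, SD 24 hours and difference 12 hours; section 5.3 gives a two-sided t-test.

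- Normal approximation: n = 2 × (1.960 + 0.842)² × 24² / 12² = 62.8, so 63 per arm.
- Exact t-test: 63.77, so 64 per arm, with power 0.801 at 64.

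The stated 64 per group reproduces and is not in dispute. It is the denominator used below.

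**2. Outcome definitions set against the visit schedule.**

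| Item in 4.8.2 | Arm counted | Can a control have it before her catheter? | What the aims and hypotheses ask |
|---|---|---|---|
| e, tracing on admission | outpatient | Yes; 3.6 has a tracing before placement | 3.2.b: adverse outcomes in both arms; 1.2.b.a: no increase over inpatient |
| g, MEU visit | outpatient | Yes; she is at home | 1.2.b.d: a small number of outpatients |
| h, SROM | outpatient | Yes; she is at home | 1.2.b.e: similar rates in the two arms |
| c, early admission for intractable pain | outpatient | No; 1.2.b.b ties the pain to the catheter | 1.2.b.b: a small number of outpatients |

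Items e, g and h have a usable control count. Item c does not. Item h shows the clearest mismatch: a two-arm hypothesis with a one-arm outcome.

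**3. What a one-arm count can say.** The documents give no rates for these events, so the counts and rates from here on are assumptions.

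- 3/64 = 4.7%, Clopper-Pearson 95% CI 1.0% to 13.1%.
- 10/64 = 15.6%, CI 7.8% to 26.9%.
- Events expected from background alone: 64 × 0.02 = 1.3; 64 × 0.05 = 3.2; 64 × 0.10 = 6.4.

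The count of 3 lies inside the range that background alone would produce, so it neither shows nor excludes an effect.

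**4. What a two-arm count adds.** For a outpatient events and b control events out of 64 each, SE(log RR) = √(1/a − 1/64 + 1/b − 1/64). The risk difference uses the Newcombe interval.

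- 10 vs 3: SE = √(0.1000 + 0.3333 − 0.03125) = 0.634; RR 3.33 (0.96 to 11.55); difference +10.9 points (0.2 to 22.2).
- 10 vs 10: SE = √(0.2000 − 0.03125) = 0.411; RR 1.00 (0.45 to 2.24); difference 0 points (−12.8 to +12.8).

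The same 10 outpatient events read quite differently in the two cases. With one arm they cannot be told apart.

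**5. Power with 64 per arm.** Outpatient rate detectable with 80% power:

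| Assumed control rate | Detectable outpatient rate | Difference |
|---|---|---|
| 2% | 16.1% | 14.1 points |
| 5% | 21.7% | 16.7 points |
| 10% | 29.6% | 19.6 points |
| 15% | 36.5% | 21.5 points |

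The gain is in interpretation, not in power.

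**The case against.** Four objections have force.

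*The control rate is not a pure background rate.* A reader might infer that controls supply the exact rate without a catheter. The documents do not support that. Section 3.6 describes the sheet of reasons to return, with the triage line, only for the outpatient arm. It also sends outpatients directly to the labor room if the post-placement tracing is not Category I, or if significant bleeding or membrane rupture occurs; controls have no such check that day. Section 4.5 admits an outpatient who comes to the MEU with pain and has no matching rule for a control at home. The home window may also differ: outpatients return the next morning, controls the next day at an assigned time, and an outpatient whose catheter cannot be passed is asked back in 24 to 72 hours. This stands. The contrast would be between strategies as delivered, not an isolated catheter effect.

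*Item c loses nothing.* A reader might add early admission to the list. Item c concerns pain that section 1.2.b.b attributes to the catheter, which controls do not have overnight. This stands; any-cause early admission would be a new outcome.

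*The safety question does not rest on these items alone.* A reader might infer that the trial cannot answer its safety question, or that section 5.4 is contradicted. Neither follows. Abruption, tracings requiring immediate delivery, infection, mode of delivery and the neonatal composite are not limited by arm. Section 1.2.b.d states a one-arm expectation for MEU visits, which a proportion with an interval can address. Section 5.4 refers to certain events, not all of them.

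*Power is low.* Section 5.2 already concedes this for most secondary outcomes, and step 5 above confirms it.

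Hypothesis 1.2.b.e also names no time window, so it may be meant to cover ripening after admission too. Even so, testing it needs a control count, and 4.8.2 provides none.

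**Conclusion.** The point holds for items e, g and h, and most clearly for h. For each, a randomized control count could be formed under section 3.6, yet the outcome is defined in one arm, although aim 3.2.b speaks of adverse outcomes in both arms and 1.2.b.e compares SROM rates. The consequence is a percentage that cannot be separated from background: at assumed background rates of 2% to 10%, 1.3 to 6.4 events per 64 women are expected regardless of the strategy. Counting controls would turn this into a randomized contrast with an interval, though a wide one.

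This rests on randomization taking place at the visit described in 3.6, before controls go home, and on control MEU visits being retrievable from the charts that section 4.6 already has abstracted. The documents do not say that such visits are recorded for controls, nor do they forbid it. The primary outcome, its analysis and the 64 per arm are unaffected. It is a worthwhile, inexpensive change, not a flaw that undermines the trial.

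**What to change.** In section 4.8.2, and in the matching parts of 3.2.b and 3.2.c:

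1. Count MEU visits (g) and SROM (h) in both arms from randomization to the scheduled admission time, and the tracing on admission (e) in both arms, for controls before catheter placement.
2. Add early admission for any reason in both arms over the same window.
3. Report the section 5.4 relative risk and 95% CI for these four outcomes.
4. Report separately the same-day direct admissions triggered by the post-placement checks in 3.6, because only outpatients can have them.
5. Keep early admission for intractable pain (c) as an outpatient-only descriptive item.
6. Report the length of the home window by arm, state how a deferred placement sets its end, and say that the contrast reflects the whole outpatient strategy, including its return instructions.

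The cost is a few more chart fields for 64 controls, with no new visit or procedure. The intervals will be wide and should be presented as such.
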